11.4.4 Full Immunogenicity Population

Includes all subjects in the Immunogenicity Population that:

- Have also completed follow-up examinations on Days 209 and 394; and
- Did not experience a laboratory confirmed COVID-19 illness between Day 1 and Day 394.

The Full Immunogenicity Population will be the primary population used for follow-up analyses.

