	
Clinical laboratory safety parameters, including haematology, coagulation and serum chemistry: before each dosing and Days 1, 2, 8, 29, 30, 36 and 57.
 
Safety parameters, including laboratory parameters and vital signs will be assessed by the PI or delegate, using the clinical site's criteria for acceptance ranges as guidelines in making the medical assessment. Abnormal laboratory blood and urinalysis results will be graded as mild, moderate or severe.
 
Safety measurements which in the opinion of the investigator are deemed clinically significant will be recorded as adverse events.
 
Injection site evaluation: before each dosing and approximately 30 minutes, 24 hours (Days 2 and 30), and until 7 days post injection (Days 8 and 36). Subjects will be provided instructions on how to self-assess at home daily.
 
Medical surveillance: Subjects will be monitored throughout the study by the clinical staff for adverse events, as described above. The Principal Investigator (PI) will be on site for study treatment administration and at least 30 minutes post-dose, and will be available on call for the remainder of the study.
 
Should a subject be diagnosed with laboratory confirmed COVID-19 disease at any time throughout the duration of the study, they will be instructed to contact the study site. COVID-19 infection will be a SAE, and follow-up by a trained healthcare provider will be required to document the severity of the disease.

Study Exit Procedures (Day 394):	AE monitoring. A blood sample will be taken to assess the magnitude and duration of the immune response to the vaccine.
Analytical Methods for Humoral and Cellular Immune Response:	
Analysis of the humoral response for SARS-CoV-2 at pre-dose, Days 15, 29, 43, 57, 209, and 394; (i) ELISA for antigen specific immune response (ii) virus based neutralisation assay (PBNA), and (iii) antibody dependent cellular cytotoxicity (ADCC) that will include assessment of potential correlates of protection
 
The induction of antigen specific T-cells will be assessed through the stimulation of peripheral blood mononuclear cells (PBMCs) with a vaccine specific peptide library and analysed by multi-colour flow cytometry following surface staining for CD3, CD4, CD8, and intracellular cytokine staining for IFN-γ, TNF-α, IL-2, IL-4, IL-13, IL-17a, CD107a, and Granzyme B.

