5.3 Study Objectives

Primary Safety Objective:

- To assess the safety and tolerability of SARS-CoV-2 Sclamp vaccine compared to placebo.

Primary Immunogenicity Objective:

- To assess the total serum antibody and neutralising antibody (NAb) immune responses elicited by SARS-CoV-2 Sclamp vaccine compared to placebo at Day 29 (28 days after first dose) and Day 57 (28 days after second dose).

Secondary Immunogenicity Objective:

- To compare the total serum antibody and NAb immune responses at Day 1 (baseline), Day 15, Day 29 (28 days after the first dose), Day 43, Day 57 (28 days after the second dose), Day 209 (6 months after the second dose), and Day 394 (12 months after the second dose).

Exploratory Immunogenicity Objectives:

- To follow subjects for 12 months following second study treatment administration to record infections with SARS-CoV-2 and evaluate the frequency and severity of all cases of laboratory confirmed COVID-19 disease.
- To conduct a detailed analysis of humoral and cellular immune responses elicited to Sclamp antigen upon vaccination compared to placebo and comparisons between dosing levels and across time course post-vaccination.
- Assess whether SARS-CoV-2 Sclamp vaccination can cause false positives in subsequent HIV testing. If so, assess duration and range of this response.

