5.4 Study Endpoints

Primary Safety Endpoints:

- Frequency, duration, and intensity of solicited local adverse events (AEs), including pain, redness, and induration for 7 days following each study treatment (for Days 1-3, Days 4-7 and Days 1-7).
- Frequency, duration, and intensity of solicited systemic adverse events (AEs), including fever, nausea, chills, diarrhoea, headache, fatigue, and myalgia for 7 days following each study treatment (for Days 1-3, Days 4-7 and Days 1-7).
- Frequency, duration, intensity, duration, and relatedness of unsolicited AEs through to Day 57. Frequency of Serious Adverse Events (SAEs), Medically-Attended Adverse Events (MAAEs), and any AEs leading to study withdrawal (including decision by the Principal

Investigator (PI) not to proceed with the second dose) at any time during study through to Day 394. Frequency and intensity of unsolicited AEs through to Days 57, 209, and 394

Primary Immunogenicity Endpoints:

- Geometric mean titre (GMT) of the serum antibody response to the Sclamp antigen compared to placebo by antigen specific ELISA at Day 29 (28 days after first dose) and Day 57 (28 days after second dose).
- GMT of the serum NAb titres to SARS-CoV-2 virus compared to placebo by MN assay at Day 29 (28 days after first dose) and Day 57 (28 days after second dose).

Secondary Immunogenicity Endpoints:

- Proportion of subjects with ≥ 4 fold increase in titre above baseline by ELISA at Days 15, 29, 43, 57, 209, and 394 post-first study treatment administration compared to placebo.
- Proportion of subjects with ≥ 4 fold increase in titre above baseline by MN assay at Days 15, 29, 43, 57, 209, and 394 post-first study treatment administration compared to placebo.
- GMT of the serum antibody response to the Sclamp antigen compared to placebo by antigen specific ELISA at Days 1, 15, 29 (28 days after first dose), and Days 43, 57 (28 days after second dose) and Days 209 and 394 (6 and 12 months post-second dose respectively).
- GMT of the serum NAb titres to SARS-CoV-2 virus compared to by MN assay at Days 1, 15, 29 (28 days after first dose), and Days 43, 57 (28 days after second dose) and Days 209, 394.

Exploratory Immunogenicity Endpoints:

- Proportion of subjects experiencing laboratory confirmed SARS-CoV-2 infection and/or severity graded COVID-19 disease between Days 57 and 394 compared to placebo.

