11.4.2 Safety Population

Includes all trial subjects that:

- Provide consent; and
- Are randomized; and
- Receive at least one dose of the study treatment, and
- Provided any evaluable safety data.

The Safety Population will be used for all safety analyses and will be analysed as actually treated.

11.4.3 Immunogenicity Population up to Day 57

Includes all subjects in the Safety Population that:

- Have immunological results for Days 1, 15, 29, 36, 43, and 57 (subjects who withdraw early and do not complete all assessment days will still be included for analyses); and
- Did not experience a laboratory confirmed COVID-19 illness between Day 1 and Day 57; and
- Did not receive any prohibited medication during the study to Day 57 that is medically assessed to potentially impact the immune response (and immunogenicity results); and
- Have no major protocol deviations affecting the primary immunogenicity outcomes as determined by the Sponsor prior to database lock and unblinding.

The Immunogenicity Population will be the primary population used for immunogenicity analyses for the Day 57 analyses for each of Part 1 and Part 2.

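### The population named primary for follow-up analyses excludes laboratory confirmed COVID-19 illness to Day 394, so the confirmed-disease part of the Day 57–394 endpoint is zero in every arm by construction

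*Protocol*

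**What the plan says.** Section 5.3 sets an exploratory objective: to follow subjects for 12 months after the second dose, record SARS-CoV-2 infections and "evaluate the frequency and severity of all cases of laboratory confirmed COVID-19 disease". The matching endpoint in Section 5.4, and in the synopsis, stands under the exploratory immunogenicity heading: "Proportion of subjects experiencing laboratory confirmed SARS-CoV-2 infection and/or severity graded COVID-19 disease between Days 57 and 394 compared to placebo".

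Section 11.4.4 defines the Full Immunogenicity Population as the members of the Immunogenicity Population who meet two further conditions: "Have also completed follow-up examinations on Days 209 and 394" and "Did not experience a laboratory confirmed COVID-19 illness between Day 1 and Day 394". It then gives the set its role: "The Full Immunogenicity Population will be the primary population used for follow-up analyses". The parent set in Section 11.4.3 already requires that a subject "Did not experience a laboratory confirmed COVID-19 illness between Day 1 and Day 57".

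On safety, Section 11.4.2 states: "The Safety Population will be used for all safety analyses and will be analysed as actually treated". The synopsis, under Subject Monitoring, adds that "COVID-19 infection will be a SAE". Section 11.5 lists the immunogenicity analyses (titres, seroconversion, fold increases, T cells, ADCC, domain specificity, isotypes). The infection/disease endpoint is not among them.

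**The concern.** The endpoint counts COVID-19 cases during follow-up. The set named primary for follow-up analyses is defined by the absence of those cases. Removing naturally infected subjects makes sense when the outcome is a vaccine-induced titre, because infection would raise it. When the outcome is the infection or disease itself, the same rule selects on the outcome.

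What is at stake is the only endpoint in the protocol defined on COVID-19 disease. Its objective asks for all laboratory confirmed cases and their severity. A table built to the stated rule would show no confirmed disease in any arm, whatever happened, and the comparison with placebo would carry no information.

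**Working it through.** **1. The endpoint set against the rule**

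| Item | Section | Content |
|---|---|---|
| Endpoint window | 5.4 | Days 57 to 394 |
| Exclusion window | 11.4.4 | Days 1 to 394, laboratory confirmed illness |
| Completer condition | 11.4.4 | Days 209 and 394 both completed |
| Class of endpoint | 5.4, synopsis | Exploratory immunogenicity |
| Role of the set | 11.4.4 | Primary for follow-up analyses |
| Other set assigned to this endpoint | none found | – |

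Let E be the subjects with laboratory confirmed COVID-19 illness in Days 57–394, and X those with such illness in Days 1–394. E lies inside X. The Full Immunogenicity Population contains no member of X, so it contains no member of E. The count of laboratory confirmed disease is 0/n in each arm, independent of attack rate, vaccine effect and sample size.

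**2. The rule applied to hypothetical subjects**

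- Vaccinee, PCR-confirmed symptomatic COVID-19 on Day 150: excluded.
- Placebo subject, the same on Day 300: excluded.
- Subject who withdraws after confirmed COVID-19 on Day 180: excluded twice, by illness and as a non-completer.
- Completer with a positive PCR and no illness: stays in and can count as an infection.
- Completer diagnosed only by the Appendix I checklist, without laboratory confirmation: stays in.

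So the zero is exact for laboratory confirmed illness and not for the whole endpoint.

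**3. Planned numbers**

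The cohort sizes in Section 8.2 sum to 32 + 32 + 56 + 32 + 32 + 32 = 216, as stated. Active: 7 groups × 24 = 168. Placebo: 6 × 8 = 48.

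**4. Size of the loss**

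The protocol gives no attack rate, so the rate *a* of confirmed illness in Days 57–394 is an assumption, taken here as equal in all arms. Expected cases = n × *a*. Chance of at least one case = 1 − (1 − *a*)^216.

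| Assumed *a* | Active (168) | Placebo (48) | P(at least one of 216) | Counted in the Full Immunogenicity Population |
|---|---|---|---|---|
| 0.5% | 0.84 | 0.24 | 0.66 | 0 and 0 |
| 1% | 1.68 | 0.48 | 0.89 | 0 and 0 |
| 2% | 3.36 | 0.96 | 0.99 | 0 and 0 |
| 5% | 8.40 | 2.40 | above 0.99 | 0 and 0 |

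With unequal assumed rates of 5% on placebo and 2% on active, 48 × 0.05 = 2.4 and 168 × 0.02 = 3.36 cases would be expected. Both would again be shown as zero.

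**5. What could remain**

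If a share *s* of detected confirmed infections is not classed as illness, the remaining infections number (illness cases) × *s*/(1 − *s*). At 5%/2% and an assumed *s* of 0.2, that is 2.4 × 0.25 = 0.6 on placebo and 3.36 × 0.25 = 0.84 on active. The Schedule of Events has no scheduled SARS-CoV-2 test after Day 29. Later tests are ad hoc, prompted by symptoms or close contact (Section 9.10.6.7 and Schedule of Events, footnote 7), so *s* is likely to be small.

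**The case against.** **The sentence may mean assay analyses only.** The name of the set suggests this. Section 11.4.2 also gives all safety analyses to the Safety Population, so Section 11.4.4 cannot cover every follow-up analysis without contradicting it. That is a fair reading, and it shows that follow-up safety is unaffected. It does not free this endpoint: Section 5.4 files it under immunogenicity, so even a limit to follow-up immunogenicity analyses still takes it in. Only an explicit limit to assay results would release it, and the text has none. Its absence from the list in Section 11.5 leaves it without any other home.

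**The cases are not hidden.** This stands. COVID-19 infection is to be handled as an SAE with its severity documented. Section 11.1 follows SAEs to study completion, tabulates adverse events by vaccination group and provides a separate SAE summary, and the Safety Population carries neither a COVID-19 exclusion nor a completer condition. A reader might infer that the report would show no COVID-19 in any arm and so lend false support to protection or to the absence of enhanced disease. The protocol does not support that inference: the SAE tables would show the cases. They are not, however, the severity-graded Day 57–394 proportion compared with placebo that Section 5.4 defines.

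**The endpoint is wider than the exclusion.** This also stands. A reader might infer that the whole endpoint is zero, but infections not classed as illness could still be counted.

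**The SAP can settle it.** Section 11 lets the SAP supersede the protocol, and the SAP was not available to this review. Choosing a population for an exploratory endpoint is ordinary SAP content. But the protocol is not silent here: it states a rule that defeats its own endpoint. The study team is unblinded after the Day 57 data are complete (Section 9.3), so a population chosen after that would be chosen with treatment known.

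**Conclusion.** The point holds for the laboratory confirmed disease component. Under Section 11.4.4 it is zero in every arm by construction, and 100% of confirmed illnesses in the window leave this endpoint and its placebo comparison. This follows from the definitions alone and rests on no assumed rate. The expected numbers lost (about 0.8 to 8.4 active and 0.2 to 2.4 placebo) do rest on an assumed attack rate of 0.5% to 5%.

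Severity is moderate. The endpoint is exploratory, Section 8.2 reports no power calculation and Section 11.3 sets no success rule. With so few placebo cases expected, the comparison would be imprecise in any population. No primary or secondary endpoint changes, and safety reporting of the cases is intact.

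**What to change.** 1. In Section 11.4.4, limit the Full Immunogenicity Population to follow-up titre and other assay analyses, where excluding natural infection is reasonable.
2. In Section 11.4.2 or 11.5, state that the Day 57–394 infection/disease endpoint is analysed in the Safety Population, with no COVID-19 exclusion and no requirement to complete Days 209 and 394.

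A rate per person-time beside the proportion is optional. It would allow for subjects who leave early.

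Cost: two sentences in the protocol, mirrored in the SAP. No new data or visits are needed, and the follow-up titre analyses are unchanged.

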11.5 Immunogenicity Analysis

For the evaluation of immunogenicity, vaccine antibody titres will be analysed using the Immunogenicity Population and the methodology described previously in Section 11:

- Geometric Mean Titres (GMT) on Days 1, 15, 29, 43 and 57, and 209 and 394 will be summarized using descriptive statistics by treatment group compared to placebo;
- Seroconversion on Days 15, 29, 43, 57, 209 and 394, compared to placebo. Seroconversion is defined as the percentage of subjects with a ≥ 4 fold increase in post-vaccination titre compared to Day 1;
- Geometric Mean Fold increases on Day 15 / Day 1, Day 29 / Day 1, Day 43 / Day 1, and Day 57 / Day 1, Day 209 / Day 1, and Day 394 / Day 1, compared to placebo;
- Fold increase in antigen specific CD4+ T-cells at Days 8, 15, 29, 36, 43, and 57 compared to Day 1 for vaccine antigen dose versus placebo;
- Fold increase in antigen specific CD8+ T-cells at Days 8, 15, 29, 36, 43, and 57 compared to Day 1 for vaccine antigen dose versus placebo;
- Fold increase in antibody dependent cellular cytotoxicity (ADCC) at Days 15, 29, 43, 57, 209, and 394 compared to Day 1 for vaccine antigen dose versus placebo;
- Fold increase in antibodies elicited to the Receptor Binding Domain (RBD), N-Terminal Domain (NTD), and clamp trimerization domain on Days 15, 29, 43, 57, 209, and 394 compared to Day 1 for vaccine antigen dose versus placebo; and
- Fold increase in antigen specific humoral immune responses including isotypes IgM, IgA, IgE, and subtypes IgG1, IgG2, IgG3 and IgG4 at Days 15, 29, 43, 57, 209, and 394 compared to Day 1 for vaccine antigen dose compared to placebo.

Once all subjects have completed Day 57, an interim analysis will be performed. The immunogenicity analysis will be included as part of this interim analysis.

12. Final Report

A final report including clinical, bioanalytical, and statistical sections will be the responsibility of Delve Medical Writing and will be signed and approved by at least the Sponsor.

An interim analysis will be performed once all Part 1 subjects (Cohorts 1,2 &3) have completed Day 29, and immunology assays for all samples up to Day 29 are completed. A brief study status report will be prepared and will discuss the safety, tolerability and immunogenicity data following a single vaccination dose. A further interim analysis will be performed once all Part 1 subjects (Cohorts 1,2 & 3) have completed Day 57, and immunology assays for all samples up to Day 57 are completed. The Final CSR will be written in an unblinded manner following the completion of the Active Study Period Evaluation Visit (Day 57) and will discuss the safety, tolerability and immunogenicity data collected during the Active Study Period. (The period from first dose up until completion of the Day 57 assessments defines the Active Study Period). The immunology assessments to be included for the Active Study Period in the CSR are the GMT of the serum antibody response (ELISA) to the Sclamp antigen and the serum NAb response by MN assay at Days 29 and 57 i.e. 28 days after the first and second dose respectively, the proportion of subjects with a ≥ 4 fold increase in titre above baseline by ELISA at Days 15, 29, 43 and 57 compared to

placebo, and the proportion of subjects with a ≥ 4 fold increase in titre above baseline by MN assay at Days 15, 29, 43 and 57 compared to placebo.

An interim analysis will be performed once all Part 2 subjects (cohorts 4,5 and 6) have completed Day 57, and immunology assays for all samples up to Day 57 are completed. An addendum to the Final CSR will be written following the completion of the Active Study Period Evaluation Visit (Day 57) for Part 2 subjects and will discuss the safety, tolerability and immunogenicity data collected during the Active Study Period.

Addenda to the final study report will be written following the 6 month follow-up visit (Day 209) and the 12 month follow-up visit (Day 394). These addenda will discuss the safety and immunogenicity data collected at the 6 month follow-up visit (the period between the Active Study Period and the 6 month follow-up visit) and the 12 month follow-up visit (the period between the 6 month follow-up visit and the 12 month follow-up visit).

In the event that the study is prematurely terminated, Delve Medical Writing will produce an abbreviated safety report. In such an event, raw data will not be submitted with the abbreviated report but will be archived at the clinical site, unless requested by the Sponsor.

13. Regulatory Considerations and Quality Assurance

13.1 Independent Ethics Committee Approval of Protocol and Other Study Documents

The Investigator(s) agree to provide the HREC with all appropriate documents, including a copy of the protocol/amendments, ICFs, advertising text (if any), Investigator's Brochure and any other written information provided to study subjects. The trial will not begin until the Investigators have obtained the HREC favourable written approvals for the above-mentioned study documents. A properly executed written ICF shall be read, signed, and dated by each subject prior to entering the trial or prior to performing any study procedure. The original signed and dated ICF will be kept at the clinical site, and a copy will be given to the subject.

In the event that the protocol is amended, the revised protocol must be approved by the HREC prior to its implementation, unless the changes involve only logistical or administrative aspects of the trial. If a revised ICF is introduced during the study, each subject's further consent must be obtained. The new version of the ICF must be approved by the HREC, prior to subsequently obtaining each subject's consent.

The Investigator and the Sponsor's representative must sign the protocol and its amendments (if any) before initiating the study.

It is the Sponsor's responsibility to submit the protocol and its amendments (if any), and the ICFs to regulatory authorities when necessary.

13.2 Compliance

This study will be conducted in compliance with the protocol, GCP, the requirements of Directive 2001/83/EC Annex I, as amended by Directive 2003/63/EC and Directive 2001/20/EC, and all applicable regulations. The study will also be conducted in compliance with the recommendations

laid down in the most recent version of the Declaration of Helsinki, with the exception that registration of such Phase 1 trials in a publicly accessible database is not mandatory.

13.3 Quality Assurance Program

Syneos Health has established Quality Control (QC) and Quality Assurance (QA) systems with written SOPs to ensure that the study will be conducted and data will be generated, recorded, and reported in compliance with the protocol, GCP, and applicable regulatory requirements. A rigorous QC program is applied to ensure accuracy of all data and reports. QA oversees a complementary risk-based program of audits to assure compliance with applicable regulations and Syneos Health's prescriptive documentation.

- 4 FDA Guidance for Industry – Toxicity Grading Scale for Healthy Adult and Adolescent Volunteers Enrolled in Preventative Vaccine Clinical Trials. Revised date 17 May 2019. Accessible online: <https://www.fda.gov/media/73679/download>
- 5 Committee for Medicinal Products for Human Use (CHMP), EMA. Guideline on strategies to identify and mitigate risks for first-in-human and early clinical trials with investigational medicinal products. EMEA/CHMP/SWP/28367/07 Rev. 1. 20 July 2017. Accessible online: https://www.ema.europa.eu/en/documents/scientific-guideline/guideline-strategies-identify-mitigate-risks-first-human-early-clinical-trials-investigational_en.pdf

Appendix I Checklist for Medical History Follow-Up for Persons Who Meet the Protocol Defined COVID-19 Case Definition.

Clinical Diagnostic Category	Sign/symptom	Outcome (please check box)	
A. At least one sign or symptom of lower respiratory tract disease:	New onset persistent dry (non-productive) cough		
	New onset tachypnoea or dyspnoea or low oxygen saturation		
B. Fever or history of fever (defined as body temperature of >38.0 °C irrespective of method)	Fever as per definition	Fever as defined in Category B	
C. At least one sign or symptom of viral illness:	New onset myalgia		
	New onset chills		
	Sore throat		
	New onset loss of smell or taste		
	Diarrhoea		
Meets Criteria for COVID-19 Clinical Disease		At least 2 of 3 clinical diagnostic categories checked	
